1.3 Hypothesis and Study Aims

The overarching hypothesis is that VTEL high-intensity functional circuit exercise in older HIV+ Veterans will improve the advanced aging phenotype and attenuate DNAm epigenetic processes underlying aging. We will explore the use of DNAm Age as an innovative biomarker that can predict adaptation to exercise by testing its association with exercise outcomes. Our experimental approach includes a 12-week VTEL exercise intervention in 80 older HIV+ Veterans who are randomized to exercise or standard of care sedentary control groups with the specific aims:

AIM 1. To determine the effect of VTEL exercise compared to control on:

- 1.1 Cardiorespiratory fitness, anaerobic threshold, and O₂pulse based on gas exchange at peak exercise
- 1.2 Sarcopenia defined by the European Working Group on Sarcopenia⁴⁴
- 1.3 Frailty defined by the Fried Phenotype⁴⁵ and the Veterans Aging Cohort Study (VACS) Index²⁷

AIM 2. To investigate the effect of VTEL exercise on DNAm Age²⁰ as a biomarker of advanced aging

AIM 3. To determine the effect of VTEL exercise on systemic inflammation by measure of:

- 3.1 DNA methylation of genes encoding pro-inflammatory cytokines in leukocytes (transcriptional regulation)
- 3.2 Corresponding systemic levels of pro-inflammatory cytokines IL-6 and IL-18 (protein expression)

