Phenotypic Outcomes (AIM 1) and Biomarker DNA Age (AIM 2): We hypothesize that the VTEL high-intensity circuit exercise intervention will increase cardiorespiratory fitness and decrease sarcopenia and frailty (AIM 1) and decrease DNA Age (AIM 2). ANOVA models will be used with dependent variables of cardiorespiratory fitness (VO₂peak, 2-minute step test) and DNA Age (years). Logistic or multinomial models will be used with dependent variables of sarcopenia (present/not present) and frailty (robust/pre-frail/frail). Secondary analyses will be performed that use the individual components of composite outcome as their own dependent variable (e.g., lean mass and strength from sarcopenia). ANCOVA will be used to test for between group difference by time (pre/post exercise). Baseline performance and demographic and clinical characteristics will be included in models to assess and adjust for known potential confounding factors based on our experience with older HIV+ adults. We do not expect significant variability or effect from HIV-related factors (e.g., antiretroviral therapy, viral load) since we will use our previous established eligibility criteria. We do not anticipate needing to adjust for sex or race since each individual will function as their own control. Nutritional analyses of macro and micronutrients will be performed to measure any change during the study, and if present, will be tested for within group and between group effects. A similar approach will be applied to smoking exposure, which will be quantitated at baseline and follow-up testing. Treatment fidelity will be measured as percent of AEX time at target heart and entered in ANOVA models. For future planning, feasibility analyses will include calculation of rates for enrollment, retention, and attendance overall and by HIV group. Aggregate data will be collected on adverse events and reasons for lost to follow-up.

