Analyses will include participants who drop out before completion of the 12-week intervention period by way of multiple imputation. This intention to treat approach will investigate factors that may affect compliance and difficulty with exercise training, including soreness and medical comorbidity. If the pattern of missing data is missing completely at random, or simply at random, our multiple imputation should eliminate bias due to loss to follow-up. Because the participants will be recruited from clinic-based VA cohorts, we will be able to obtain clinical data from participants who drop out of the study, but remain in clinical care, to determine if drop-out was related to medical conditions that may influence outcomes. Thus, we will be able to estimate bias introduced by loss to follow-up. If there is sufficient information, we may be able to model the drop-out process and adjust our analyses for loss to follow-up even if the missing data pattern is non-ignorable. If 36 training sessions cannot be completed in 12 weeks, then total training time will be tracked, and incorporated into the data analysis.

DNA Methylation (AIM 3): We will examine the change of methylation levels after 12 weeks for each candidate marker using ANOVA models. To examine epigenetic association with each outcome, we will fit the linear regression model as follows: where Y_i is the quantitative outcome measurement, Z_i is the vector of covariates including age, race, smoking status and leukocyte proportions, and E_i is the candidate epigenetic marker. ANCOVA will be used to test for between group difference by time (pre/post exercise). The candidate epigenetic markers will involve individual CpG sites previously identified and discussed in detail section D4c. We will extend this linear regression model to account for batch/chip effects and

longitudinal measures using a linear mixed model. We will adjust the significance threshold for multiple testing using Bonferroni correction ($p < 0.05 / \text{number of tests}$).

Sample Size Estimates:

AIM 1. Paired t-test was used to test for a mean change given a range of correlation between pre and post values with assumptions of $\alpha = 0.05$ and 80% power. (Mean (SD) values for the VO_2peak are from our current high-intensity AEX + RT trial in HIV+ Veterans (Table 3). Data for 2-minute step test are from our VTEL Gerofit exercise program (C3). Values for chair stands are results from a 10-week RT in older men.⁴⁶ We will have adequate

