Inflammatory Biomarkers: Testing of inflammatory biomarkers will occur at each respective enrollment site using the same kits since procedures are very standardized. We appreciate that change in plasma levels of cytokines can vary greatly between and within individuals. Our analysis plan takes this point into consideration by including change in cytokines as an independent variable in models of the primary and secondary outcomes. Changes in plasma levels will be calculated pre/post intervention and will be tested for association with changes in outcomes as well as between group differences.

DNA Methylation Assay: Samples will be tested for DNA methylation in the laboratory of [name] in Atlanta using established methods as previously described.^{23,58,78} Samples from Baltimore participants will be shipped directly to [name] lab. In sum, [name] will conduct a comprehensive interrogation of epigenome-wide CpG sites using the Illumina Infinium Methylation EPIC (850K) BeadChip. The 850K chip covers 99% of the NCBI Reference Sequence (RefSeq) genes, with sites covering the promoter, untranslated regions, and gene body, >95% of CpG islands, enhancer regions from FANTOM5 and ENCODE, as well as differentially methylated sites across tissue types. The EZ DNA Methylation Kit (Zymo Research, Orange CA) will be used to bisulfite-convert 0.5 µg of gDNA per sample. Bisulfite-converted DNA samples will be whole-genome amplified, enzymatically fragmented, and purified. Samples will be hybridized to the array. The array will then be fluorescently stained, scanned, and assessed for fluorescence intensities to quantify the methylation levels of each DNAm site.

Blood Banking: Blood sampling will include additional volume for future testing related to cardiometabolic disease and aging. These samples will be stored at the Atlanta and Baltimore VAMCs.

Clinical Data: Medical history and clinical laboratory values will be collected at the eligibility visit by a research clinician. Data will include comorbid conditions, medication use, CD4 cell count and HIV-1 PCR level, and other clinical labs included in the VACS Index. Both the participant and review of medical records will be used as source of the data.

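### The between-arm analysis of IL-6 and IL-18 (Aim 3.2) states neither a scale nor a baseline term; read literally on skewed data, it gives up power

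*Combined protocol and SAP*

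**What the plan says.** Section 1.3 makes the effect of exercise on systemic IL-6 and IL-18 a named sub-aim (3.2). High-sensitivity CRP is not in that sub-aim; it appears in Table 7 among examples of inflammation biomarkers.

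Section 3.3.b (Inflammatory Biomarkers) is the only text on how these markers will be analysed. It says that changes in level "will be calculated pre/post intervention and will be tested for association with changes in outcomes as well as between group differences". It recognises that "change in plasma levels of cytokines can vary greatly between and within individuals", and says the analysis plan deals with this by "including change in cytokines as an independent variable in models of the primary and secondary outcomes".

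Section 2.3.e gives IL-6 and IL-18 no model of their own. Two of its statements might bear on them:

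- The Aim 3 paragraph, headed DNA methylation, says "ANCOVA will be used to test for between group difference by time (pre/post exercise". It names no cytokine. The covariates it lists for the regression on epigenetic markers are age, race, smoking and leukocyte proportions, with no baseline value of the outcome.
- The paragraph on Aims 1 and 2 says "Baseline performance and demographic and clinical characteristics will be included in models to assess and adjust for known potential confounding factors". It does not cover Aim 3.

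No log transformation, rank method or outlier rule for cytokines appears anywhere.

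**The concern.** The plan names change in plasma level as the variable to compare between arms and leaves two choices open: the scale, and whether baseline enters the model. Both affect power.

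- **Scale.** If concentrations are right-skewed, variability on the original scale rises with the level. The few participants with high values then dominate the variance of the mean change. A proportional effect is easier to detect on the log scale.
- **Baseline.** An unadjusted change score fixes the baseline coefficient at 1. ANCOVA estimates it, and is more efficient whenever the pre/post correlation is below 1.

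The plan's own answer to cytokine variability does not reach this test. Using cytokine change as a predictor of other outcomes does nothing for the comparison of cytokines between arms. At stake is whether Aim 3.2 can detect a real reduction. Leaving the choice open also lets it be made after the data are seen.

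**Working it through.** **Plan figure to reproduce.** There is none. Section 2.3.e gives no sample size, effect or power for IL-6 or IL-18; its Aim 3 figure of 34 participants concerns methylation.

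**Inputs from the documents**

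- 40 randomised per arm (3.1) and 30% attrition (3.3.a), so 40 × 0.70 = 28 per arm. Table 5 instead projects 80 completers, that is 40 per arm, so both are shown.
- Alpha 0.05, taken as two-sided (2.3.e does not say).
- Pre/post correlation r = 0.3, 0.5, 0.7: the range in the sample-size table, which is not given for cytokines.

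**Assumptions, not in the documents.** Levels are lognormal with equal SD at both visits, SD of the log level is 0.5, 0.7 or 0.9, and exercise lowers levels by 30% (ratio 0.70).

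**Step 1: baseline adjustment alone, no skewness.** With SD s, the per-person variance behind the arm contrast is 2(1 − r)s² for change and (1 − r²)s² for ANCOVA. The ANCOVA/change ratio is (1 + r)/2. For an effect that ANCOVA detects with 80% power, change-score power is Φ(2.80 × √((1 + r)/2) − 1.96).

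| r | (1 + r)/2 | Sample saved by ANCOVA | Power, ANCOVA | Power, change |
|---|---|---|---|---|
| 0.3 | 0.65 | 35% | 80% | 62% |
| 0.5 | 0.75 | 25% | 80% | 68% |
| 0.7 | 0.85 | 15% | 80% | 73% |

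Omitting baseline therefore costs 18, 12 and 7 points.

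**Step 2: adding skewness.** Simulated power at 28 per arm with a true ratio of 0.70 (40,000 runs per cell):

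| Log SD | r | Raw change | Raw ANCOVA | Log change | Log ANCOVA |
|---|---|---|---|---|---|
| 0.5 | 0.3 | 46% | 72% | 61% | 78% |
| 0.5 | 0.5 | 59% | 79% | 75% | 85% |
| 0.5 | 0.7 | 78% | 91% | 92% | 95% |
| 0.7 | 0.3 | 24% | 41% | 35% | 50% |
| 0.7 | 0.5 | 31% | 46% | 47% | 57% |
| 0.7 | 0.7 | 45% | 60% | 68% | 74% |
| 0.9 | 0.3 | 14% | 24% | 24% | 33% |
| 0.9 | 0.5 | 18% | 27% | 31% | 38% |
| 0.9 | 0.7 | 25% | 35% | 47% | 52% |

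Independent repeats agree to about a point: the lowest raw-change cell comes out at 13–14%, and raw ANCOVA at log SD 0.7, r = 0.5 at 46–47%.

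**Check by formula at log SD 0.7, r = 0.5.** The effect is |ln 0.70| = 0.357.

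- Log ANCOVA: SE = 0.7 × √(0.75 × 2/28) = 0.162, and 0.357/0.162 − 1.96 = 0.24, giving about 60%.
- Log change: SE = 0.7 × √(1 × 2/28) = 0.187, and 0.357/0.187 − 1.96 = −0.05, giving about 48%.

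The simulated 57% and 47% are slightly lower, as expected from t rather than normal quantiles.

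**Step 3: 40 per arm, log SD 0.7, r = 0.5.** Raw change 40%, raw ANCOVA 61%, log change 61%, log ANCOVA 73%.

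**Step 4: no effect.** Over these log SDs and correlations, the raw-change test rejects in 4.3–5.0% of runs, at 28 and at 40 per arm.

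**The case against.** A reader might infer that the plan commits to raw, unadjusted change. The documents do not say that. Neither the scale nor the absence of a baseline term is stated; both readings come from silence. Change can be computed on logs. ANCOVA of change with baseline as a covariate gives the same treatment effect as ANCOVA of the follow-up value, so naming change does not by itself exclude baseline adjustment. Aim 3 includes 3.2, so the ANCOVA sentence in the Aim 3 paragraph may have been meant to cover cytokines. This stands: the defect is an unspecified and possibly inconsistent analysis, not a declared wrong one.

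If that sentence does apply with a baseline cytokine term, the gain left from the log scale is smaller: 11 points at log SD 0.7 and r = 0.5, 4–6 points at log SD 0.5, and 9–17 points at log SD 0.9. It does not vanish, and the scale would still be unstated.

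The size also rests on a skewness and an effect the documents do not give. At log SD 0.3, raw change already has about 90% power or more for the same effect. The comparison assumes a proportional effect; an additive one would favour the log scale less.

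A reader might also infer that a few extreme values would produce false positive findings. The null runs do not support that. Finally, the plan states no power for Aim 3.2, so no claim in it is contradicted.

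**Conclusion.** The point holds as a gap in specification with a clearly better and nearly free alternative. Sections 2.3.e and 3.3.b do not together say which model, on which scale and with which baseline term will test Aim 3.2, and they should be reconciled.

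The literal reading of 3.3.b, unadjusted change on the original scale, is the weakest of the four analyses compared. Under the lognormal, 30%-reduction and 28-per-arm assumptions, its power runs from about 13–14% to 78% across log SD 0.5–0.9 and r 0.3–0.7, against 33% to 95% for log-scale ANCOVA. The part that needs no assumption about skewness is the 15–35% sample saving from baseline adjustment over the plan's own correlation range, given equal variances at the two visits. The harm is lost power only. Confidence is high that the text is silent, and lower on the size of the loss.

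**What to change.** In 2.3.e, add a model for Aim 3.2: ANCOVA of log follow-up IL-6 and log follow-up IL-18, each on arm, its own log baseline and site. Report the ratio of geometric means with its 95% CI. The site term is warranted because 3.3.b has the assays run separately at each enrollment site. Apply the same model to hsCRP, labelled as a Table 7 marker and not as part of Aim 3.2. State how values below the detection limit enter the log scale. Use log change in the analyses relating cytokine change to outcome change. Amend 3.3.b to refer to this model, and say whether the ANCOVA sentence in the Aim 3 paragraph covers cytokines.

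The cost is SAP wording; baseline and follow-up levels are already collected. The one downside is that the effect is reported as a ratio instead of an absolute difference.
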